## 6 Treatment

### 6.1 Study treatment

Novartis will supply the following study treatment:

- Cohort 1: Open-label ofatumumab in an auto-injector containing 20 mg s.c ofatumumab (20 mg/0.4ml) for subcutaneous administration as per the assessment schedules in [Table 8-1](#) and [Table 8-2](#).

Participants in Cohort 2 will continue on their commercially prescribed ofatumumab treatment.

Participants enrolled in Cohort 3 will continue on their commercially prescribed interferon or glatiramer acetate treatment.

Participants in Cohort 4 will continue on their commercially prescribed ofatumumab treatment.

Participants in Cohort 5 will continue on their commercially prescribed interferon or glatiramer acetate treatment.

Participants in Cohort 6 will continue on their commercially prescribed ofatumumab.

Participants will obtain a COVID-19 mRNA vaccine from their HCP (private insurance) or appropriate federal, state or local program.

#### 6.1.1 Investigational and control drugs

**Table 6-1 Investigational and control drug**

Investigational/ Control Drug	Route of Administration	Supply Type	Supplied by
OMB157 20mg/0.4mL	Subcutaneous Use	Open-label auto-injectors (Cohort 1); commercially prescribed (Cohorts 2, 4 and 6)	Sponsor (Cohort 1) or commercially prescribed (Cohorts 2, 4 and 6)
Interferon or glatiramer acetate	Subcutaneous or intramuscular use	Commercially prescribed	Commercially prescribed
COVID-19 mRNA vaccine (Pfizer or Moderna)	Intramuscular	Commercially supplied	HCP/private insurance, or appropriate federal, state or local program

### **6.1.1.1 Decentralized Clinical Trial Model (US sites only)**

The study medication and all required clinical study supplies may be distributed via direct-to-participant shipment utilizing an extension of the IND for compliance purposes.

### **6.1.2 Additional study treatments**

No other treatment beyond investigational drug are included in this trial.

### **6.1.3 Treatment cohorts**

- Cohort 1: RMS participants receiving non-live COVID-19 mRNA vaccine at least two weeks prior to ofatumumab start.
- Cohort 2: RMS participants receiving non-live COVID-19 mRNA vaccine at least 4 weeks after ofatumumab start.
- Cohort 3: RMS participants receiving non-live COVID-19 mRNA vaccine at least 4 weeks after start of prescribed interferon or glatiramer acetate.
- Cohort 4: RMS participants having completed a full course (2 doses) of a non-live COVID-19 mRNA vaccine  $\geq$  4 weeks after ofatumumab start.
- Cohort 5: RMS participants having completed a full course (2 doses) of a non-live COVID-19 mRNA vaccine  $\geq$  4 weeks after glatiramer acetate or interferon start.
- Cohort 6: RMS participants having completed a full course (2 doses) of a non-live COVID-19 mRNA vaccine  $\geq$  4 weeks after ofatumumab start and having received a booster  $\geq$  14 days prior to screening

### **6.1.4 Post-Trial Access**

Participants in Cohort 1 will be referred to the commercial participant services hub for post-trial continuity of treatment, where the benefit/risk is acceptable and discussed with the participant, investigator and if applicable, the participant's treating physician. Participants who do not complete the study or withdraw due to an ofatumumab related AE or SAE should follow-up with their treating physician for continued treatment options.

## **6.2 Other treatment(s)**

### **6.2.1 Concomitant therapy**

The Investigator should instruct the participant to notify the study site about any new medications he/she takes after study enrollment. All medications, procedures, and significant non-drug therapies (including physical therapy and blood transfusions) administered after the participant was enrolled into the study must be recorded on the appropriate electronic Case Report Forms (eCRFs).

Each concomitant drug must be individually assessed against all exclusion criteria/prohibited medication. If in doubt, the investigator should contact the Novartis Medical Director before randomizing a participant or allowing a new medication to be started. If the participant is already enrolled, contact Novartis to determine if the participant should continue participation in the study.

### Premedication prior to subcutaneous injection

Premedication is not required. Premedication with acetaminophen and/or antihistamines (or equivalent) is optional and may be administered at the discretion of the Investigator. If Investigators choose to administer premedication, it should be administered 30 to 60 minutes prior to study drug injection.

Any administrations of premedication must be recorded in the appropriate eCRF.

Each concomitant drug must be individually assessed against all exclusion criteria/prohibited medication. If in doubt, the investigator should contact the Novartis Medical Director before enrolling a participant or allowing a new medication to be started. If the participant is already enrolled, contact Novartis to determine if the participant should continue participation in the study.

#### 6.2.2 Prohibited medication

Use of the treatments displayed in [Table 6-2](#) is NOT allowed for any study cohort in combination with study drug, due to increased risk of immunosuppression and confounding of efficacy evaluations.

Exclusionary medications for study eligibility are listed in the exclusion criteria ([Section 5.2](#)). Use of excluded medications is not allowed for any study cohort while the participant is on study medication.

**Table 6-2      Prohibited medication**

Medication	Action taken
Immunosuppressive/chemotherapeutic medications (including herbal) or procedures, including but not limited to cyclosporine, azathioprine, leflunomide, methotrexate, cyclophosphamide, mitoxantrone, lymphoid irradiation and hematopoietic stem cell transplantation	Discontinue participant from study
Monoclonal antibodies targeting the immune system, including but not limited to natalizumab, alemtuzumab, daclizumab and B-cell depleting agents under investigation, such as but not limited to ublituximab and obinutuzumab	Discontinue participant from study
Any other immunomodulatory or disease modifying MS treatment, including but not limited to fingolimod, interferon beta, glatiramer acetate, dimethyl fumarate, intravenous immunoglobulin, plasmapheresis or systemic corticosteroids (except for when given for MS relapse treatment as defined in Section 6.2.3 )	Discontinue participant from study.
Administration of any live or live attenuated vaccine (including for measles) is prohibited while participants are exposed to study drug	They may be administered when participants are no longer exposed to

Medication	Action taken
(long lasting effects of the study drugs should be taken into consideration)	study drug. Consider risk/benefit and follow local labels.

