## **9 Discontinuation and completion**

### **9.1 Discontinuation from study treatment and from study**

#### **9.1.1 Discontinuation from study treatment**

Discontinuation of study treatment for a participant occurs when study treatment is permanently stopped for any reason (prior to the planned completion of study drug administration, if any) and can be initiated by either the participant or the investigator.

The investigator must discontinue study treatment for a given participant if, he/she believes that continuation would negatively impact the participant's well-being.

Discontinuation from study treatment is required under the following circumstances:

- Participant/guardian decision
- Pregnancy
- Total serum immunoglobulin IgG  $<$  400mg/dl after Visit 2
- Use of prohibited treatment as per recommendations as per the USPI
- Any situation in which study participation might result in a safety risk to the participant
- Diagnosis of PML
- Participants with active serious infections or reactivation

- Skin and/or mucosal reactions which raise the suspicion of severe generalized major skin reactions (Stevens-Johnson syndrome, or toxic epidermal necrolysis-Lyell's syndrome)
- Hypersensitivity to ofatumumab
- Protocol violation that results in a significant risk to the participant's safety
- Emergence of certain adverse events, such as malignancy (except successfully treated basal cell carcinoma, *in situ* squamous cell carcinoma and *in situ* carcinoma of cervix of uterus), liver failure or serious chronic infection (such as human immunodeficiency virus (HIV))
- Severe hyperproteinemia
- Non-compliance with study drug or study procedures

If discontinuation from study treatment occurs, the investigator should make a reasonable effort to understand the primary reason for the participant's discontinuation from study treatment and record this information.

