Participants who discontinue study treatment or who decide they do not wish to participate in the study further should NOT be considered withdrawn from the study UNLESS they withdraw their consent (see [Section 9.1.2 'Withdrawal of Informed Consent' section](#)). **Where possible, they should return for the EOS Visit.** At EOS visits all dispensed study drug to participants in Cohort 1 should be reconciled and the adverse event and concomitant medications should be recorded on the CRF (for participants in both cohorts). If they fail to return for these assessments for unknown reasons, every effort (e.g. telephone, e-mail, letter) should be made to contact the participant/pre-designated contact as specified in the lost to follow-up section. This contact should preferably be done according to the study visit schedule.

If the participant cannot or is unwilling to attend any visit(s), the site staff should maintain regular telephone contact with the participant, or with a person pre-designated by the participant. This telephone contact should preferably be done according to the study visit schedule.

After discontinuation from study treatment, at a minimum, in abbreviated visits, the following data should be collected at clinic visits or via telephone/email contact:

- New / concomitant treatments
- Adverse Events / Serious Adverse Events

The investigator must also contact the IRT to register the participant's discontinuation from study treatment.

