### **9.1.2 Discontinuation from study**

Discontinuation from study is when the participant permanently stops receiving the study treatment, and further protocol-required assessments or follow-up, for any reason.

Participants must be discontinued from the study under the following circumstances:

- Failure to receive a complete COVID-19 mRNA (Pfizer or Moderna) vaccination course (2 doses)
- IgG  $\leq$  400mg/dl

If the participant agrees, a final evaluation at the time of the participant's study discontinuation should be made as detailed in the assessment table under the End of Study Visit (refer to [Section 8](#)).

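### Table 6-2 takes users of most prohibited medications off the study, while Section 9.1.1 stops study treatment and keeps them in follow-up; the cost is some safety contacts and later antibody samples (minor)

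*Protocol*

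**What the plan says.** Protocol Section 6.2.2 bans the Table 6-2 treatments "due to increased risk of immunosuppression and confounding of efficacy evaluations". For immunosuppressants, for monoclonal antibodies acting on the immune system, and for other immunomodulatory or disease-modifying treatment, the action is to take the participant off the study. The third group includes "plasmapheresis or systemic corticosteroids (except for when given for MS relapse treatment as defined in" Section 6.2.3). Only the live-vaccine row carries no study exit.

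Section 9.1.2 gives that action its meaning: "Discontinuation from study is when the participant permanently stops receiving the study treatment, and further protocol-required assessments or follow-up, for any reason". Its list of mandatory exits has two entries, an incomplete two-dose vaccine course and low IgG.

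Section 9.1.1 lists "Use of prohibited treatment as per recommendations as per the USPI" among the reasons to stop study treatment. It then says that participants who stop treatment "should NOT be considered withdrawn from the study UNLESS they withdraw their consent", and SAP 1.1 repeats this. On what is still gathered: "After discontinuation from study treatment, at a minimum, in abbreviated visits, the following data should be collected at clinic visits or via telephone/email contact". Two items follow, new or concomitant treatments and AEs/SAEs. Antibody draws are not among them.

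Section 6.2.1 tells sites with doubts about a concomitant drug in an enrolled participant to contact the sponsor to "determine if the participant should continue participation in the study".

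**The concern.** A site that learns of, say, a steroid course for another indication finds two instructions. Table 6-2 ends participation. Section 9.1.1, if its entry covers the drug, ends study treatment and continues follow-up. Section 6.2.1 refers the site to the sponsor but gives no rule for deciding.

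Two things are at stake, and they differ in origin.

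- **Safety observation, due to Table 6-2.** The participants removed are those for whom Section 6.2.2 cites added immunosuppression risk. Section 6.2.3, by contrast, keeps participants who receive high-dose steroids for relapse and asks for more vigilance about infection.
- **Later antibody samples, shared with Section 9.1.1.** An early exit leaves later visit windows without a sample, and the SAP may count these as non-response in the secondary sustained-response analysis. A site that collects only the Section 9.1.1 minimum can produce the same gaps.

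**Working it through.** The plan states no figure on this point and no rate of prohibited-medication use. The results below are therefore per participant, over an assumed range of discontinuation days.

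**Inputs**
- Section 8: after premature discontinuation, the EOS visit falls within 7 days and a remote safety contact 30 days after it.
- Tables 8-1 to 8-6: the last planned contact is Day 412 (Pfizer) or Day 419 (Moderna); an antibody sample is scheduled at EOS.
- SAP 2.4.1.1: visit windows for the antibody assay.
- Protocol 12.8.1: 22 participants per cohort group.

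**Formulas**, with d the day of discontinuation
- EOS by d + 7; last contact by d + 7 + 30 = d + 37 (40 days if the +3-day visit window is used).
- Days lost = 412 − (d + 37) or 419 − (d + 37).
- Net contacts lost = tabulated contacts after d, minus the 2 that early exit provides.
- Empty windows = antibody windows after the one holding the early EOS sample.

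| d | EOS by | Last contact by | Days lost (Pfizer / Moderna) | Net contacts lost, Cohort 1 | Net contacts lost, Cohorts 2–6 | Empty later windows, Cohort 1 / 2–3 / 4–6 |
|---|---|---|---|---|---|---|
| 50 | 57 | 87 | 325 / 332 | 6 − 2 = 4 (Pfizer), 7 − 2 = 5 (Moderna) | 4 − 2 = 2 | 4 / 3 / 2 |
| 100 | 107 | 137 | 275 / 282 | 4 − 2 = 2 | 4 − 2 = 2 | 3 / 3 / 2 |
| 200 | 207 | 237 | 175 / 182 | 4 − 2 = 2 | 4 − 2 = 2 | 2 / 2 / 2 |
| 300 | 307 | 337 | 75 / 82 | 2 − 2 = 0 | 2 − 2 = 0 | 1 / 1 / 1 |

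The later windows number 4 in Cohort 1 and 3 in the other cohorts. Window counts are the same for both vaccines.

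**Delayed detection.** The 7 days run from discontinuation, not from use. In Cohorts 2 and 3 (Pfizer) no visit is tabulated between Day 36 and Day 202. If use on Day 50 or 100 is first learned of on Day 202, EOS is due by Day 209 and the last contact by Day 239. The loss is then 412 − 239 = 173 days, 3 − 2 = 1 contact and 2 windows.

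**Effect on a late response rate**
- SAP 2.6.3 and 2.6.4, read as applying at each time point: one removed participant lowers the rate by at most 1/22 = 4.5 percentage points. If the chance of a positive late sample were 50%, 70% or 80% (assumed), the expected loss is 0.50/22 = 2.3, 0.70/22 = 3.2 or 0.80/22 = 3.6 points.
- SAP 5.1.3.3 imputes non-response only when there is no valid assessment after both doses. A participant with an earlier valid sample is then not imputed, and the effect is 0.
- Example with one removed responder: 16/22 = 72.7% (exact 95% CI 49.8 to 89.3) becomes 15/22 = 68.2% (45.1 to 86.1).

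**The case against.** The case for leaving the text alone has several parts.

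- **The conflict is softer than it looks.** The Section 9.1.1 entry is tied to the USPI, which is not in the documents, so its overlap with Table 6-2 is unknown. Low IgG stands in both 9.1.1 and 9.1.2, so an entry in 9.1.1 does not by itself rule out study exit. Table 6-2 could be the specific rule and 9.1.1 the general one. This stands as a qualification. It does not tell a site which rule to follow, and prohibited medication, unlike low IgG, is absent from the exit list.
- **Safety follow-up remains.** Section 10.1.1 asks for AE monitoring for at least 30 days after the last dose, which EOS plus a 30-day contact is built to meet. A detected event is followed to resolution, and SAEs are reported until 30 days after the last visit, or later if suspected to be treatment-related (Section 10.1.3). This stands: what is lost is scheduled collection after that point.
- **Removal may be deliberate.** Antibody values after a switch to another immunosuppressant no longer describe response on the original therapy. That is a fair reason to mark such values. It does not justify ending AE collection.
- **The antibody loss is not the table's alone.** This is correct, for the reason given above. The observed-case analysis in SAP 2.6.6 also partly offsets the imputation.

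A reader might infer that observation always ends 37 days after use. The documents do not support this, because the interval starts at discontinuation. A reader might also set removals against the allowance of 22 enrolled for 20 needed. That allowance is stated for the primary endpoint, and under non-response imputation the participant stays in the denominator of 22.

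**Conclusion.** The point holds and is minor. Table 6-2 and Section 9.1.1 give different instructions about follow-up after prohibited medication, and nothing in either document settles which applies.

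The losses in the table assume prompt discontinuation on the days shown; later detection reduces them. The 4.5-point ceiling per removal assumes imputation at each time point and a group of 22. How often this would happen cannot be judged from the documents.

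It would be tempting to conclude that the main result is biased. The documents do not support that. The primary time point is Visit 4 in Cohorts 1 to 3 and Visit 2 in Cohorts 4 to 6 (SAP 1.1), so mainly early use in Cohorts 1 to 3 could touch it. No hypothesis is tested (SAP 5.4.1 and 5.4.2).

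**What to change.** - Change the action in the three Table 6-2 rows to a study-treatment decision under Section 9.1.1. Keep the participant for scheduled visits, AE/SAE collection and the antibody draws already planned, unless consent is withdrawn.
- Let the prohibited-treatment entry in Section 9.1.1 refer to Table 6-2 as well as the USPI, and name the antibody draws in its follow-up data.
- Record the medication and its dates, flag antibody values obtained afterwards, and show the later time points with and without them.
- As a companion clarification, say in SAP 2.6.3 and 2.6.4 whether imputation applies at each time point or only as worded in SAP 5.1.3.3.

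The cost is a few lines of text and one analysis flag. For each affected participant discontinued on Day 50 or later, it means a net 0 to 2 more contacts in Cohorts 2 to 6 and up to 4 or 5 in Cohort 1, all already in the schedule. No new procedure is needed. The drawback is that some late antibody values will be confounded by the medication, which the display with and without them makes visible.

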### 6.2.3 Recommended treatment of MS relapse

An MS relapse is defined as an appearance of a new neurological abnormality or worsening of previously stable or improving pre-existing neurological abnormality, separated by at least 30 days from onset of a preceding clinical demyelinating event (Polman et al 2011). The abnormality must have been present for at least 24 hours and occurred in the absence of fever (< 37.5°C) or a known infection.

The decision to treat MS relapses should be based on the Investigator's judgement and/or local clinical practice. Standard of care will be followed during treatment as per local clinical practice. Taper with oral steroids is not permitted. Plasmapheresis may be used only if participant does not respond to standard treatment with corticosteroids.

If MS relapses require treatment, the standard treatment should consist of a short course of corticosteroids of 3-5 days and up to 1000mg methylprednisolone/day or equivalent on an inpatient or outpatient basis. Standard of care will be followed during treatment as per local clinical practice.

Investigators should consider the added immunosuppressive effects of corticosteroid therapy and increase vigilance regarding infections during such treatment and in the weeks following administration. Use of steroids for treatment of MS attack/relapse must be recorded on the Concomitant Medications eCRF.

### 6.3 Preparation and dispensation

Each study site will be supplied with study drug in packaging as described under investigational and control drugs section ([Section 6.1.1](#)).

A unique medication number is printed on the study medication label.

Investigator staff will identify the study medication kits to dispense to the participant by contacting the Interactive Response Technology (IRT) and obtaining the medication number(s).

### Special notes regarding dispensing treatment to Cohort 1

Participants have the option to take home multiple doses of study drug for administration at home between office visits or they may return to the study site between office visits for administration of study drug onsite. To facilitate this, Study Staff will have the option to either dispense multiple kits of study drug in IRT by selecting "home visit" or dispense 1 study drug kit for office administration by selecting "office visit". Example:

- At Visit 4 (office visit), if "home visit" is selected in IRT, sufficient study drug will be dispensed for administration during the Visit 4 office visit plus sufficient study drug for at-home administrations until the participant returns for the Visit 8 office visit. If "office visit" is selected, the system will only dispense study drug for administration in the office during Visit 4. In this case, the patient will need to return to the site a week later to

receive their next scheduled dose at which time the Study Staff will need to contact IRT again to dispense treatment and select either “home visit” or “office visit”.

- At Visit 9 (office visit), participants will **not** receive a dose of study drug in the office but will receive sufficient study drug to cover monthly, at-home administrations of study drug until the Visit 10 office visit.
- At Visit 10 (office visit), participants will **not** receive a dose of study drug in the office but will receive sufficient study drug to cover the next 3 monthly, at-home administrations of study drug.

If a participant in Cohort 1 is unable to travel to the investigative site for their study visit, shipment of study treatment from the site to the participant’s home may be an option. As per **Section 4.6**, during a Public Health emergency as declared by Local or Regional authorities i.e. pandemic, epidemic or natural disaster, that limits or prevents on-site study visits, delivery of IMP directly to a participant’s home may be permitted (if allowed by Local or Regional Health Authorities and Ethics Committees as appropriate) in the event the Investigator has decided that an on-site visit by the participant is no longer appropriate or possible, and that it is in the interest of the participant’s health to administer the study treatment even without performing an on-site visit. The dispatch of IMP from the site to the participant’s home remains under the accountability of the Investigator. Regular phone calls or virtual contacts every month should occur between the site and the participant for instructional purposes, safety monitoring, investigation of any adverse events, ensuring participants continue to benefit from treatment, and discussion of the participant’s health status until the participants can resume visits at the study site.

